Usual care will consist of any treatment(s) (including no treatment) other than and exanet initiated within 3 hours post-randomization that the Investigator and/or other treating physicians consider to be appropriate. For and exanet treatment, patients will receive one of two dosing regimens of and exanet based on which FXa inhibitor they received (see Section 6.2) and the amount and timing of the most recent dose.

Andexanet dosing should be initiated no later than 30 minutes after randomization and preferably within 2 hours of the baseline brain imaging scan (Figure 1). To accommodate dosing within 2 hours of the baseline scan closest to randomization, reconstitution of andexanet prior to randomization will be allowed. Andexanet will be given as an intravenous (IV) bolus administered over ~15 minutes (low dose) to 30 minutes (high dose), followed immediately by continuous infusion administered over ~120 minutes. There will be no cross-over between

treatment groups. Patients may be treated for bleeding with any unplanned rescue medications or intervention deemed to be clinically warranted, except andexanet in the usual care arm (see Section 7.2, Section 7.3, and Section 7.4 for specific guidance on use of rescue and concomitant medications).

It is intended that all patients initiate treatment as soon as possible after randomization. Patients allocated to and exanet arm should commence and exanet no later than 30 minutes post-randomization and preferably within 2 hours of the baseline brain imaging scan. A schematic for events of a patient's involvement in the study from baseline through approximately 12 hours after randomization can be found in Figure 1.

- 1 Blinded evaluation at 12 hours and 24 hours post-randomization
- 2 Reconstitution of andexanet prior to randomization will be allowed. Initiation of dosing should occur no later than 30 minutes after randomization and preferably within 2 hours of the baseline head scan.

CT = computed tomography; FXa = Activated Factor Xa; GCS = Glasgow Coma Scale; h = hour; labs = laboratories; min = minutes, MRI = magnetic resonance imaging; mRS = modified Rankin Scale; NIHSS = National Institutes of Health Stroke Scale; TFPI=Tissue Factor Pathway Inhibitor; TG = thrombin generation

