Note: Dosing procedures begin after randomization. Andexanet will be given as a bolus over 15-30 minutes followed by 120-minute continuous infusion. Treatment duration of usual care is dependent upon available therapy. A detailed listing of study procedures, including additional laboratory samples Day 1 through Day 30 is detailed in Appendix A.

Following baseline assessments, imaging evaluation will be performed at approximately 12 hours following randomization. All scans for individual patients should utilize a consistent imaging modality, scanner, and acquisition protocols/techniques whenever possible. Primary neurologic assessment will consist of evaluation of the National Institutes of Health Stroke Scale (NIHSS) at baseline and at 12 hours. The 12-hour and 24-hour assessments will be performed by study personnel who are blinded to the treatment allocation of the patient. Additional NIHSS measurements performed at 2 hours, 3 hours, 6 hours, and 72 hours will be performed for safety monitoring purposes; these measurements may be blinded or unblinded. Following the 12-hour assessment, patients will return for a follow-up visit at Day 30 (+7) and follow-up phone calls on Day 7 (+3) and Day 14 (+6). s (a detailed Schedule of Activities is provided in Appendix A). An additional visit is required for patients with a positive anti-andexanet antibody response at the Day 30 visit approximately 120 days post-randomization, or within 30 days of when the positive test is made known to the Investigator, whichever is later.

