5.4. Secondary Endpoint Analysis

The secondary objective of this study is to evaluate the effect of and examet versus UC on anti-fXa activity. The secondary endpoint is the percent change in anti-fXa activity from baseline to nadir during the first 2 hours post-randomization.

Analyses for anti-fXa activity will be based on the ITT Set. Change and percent change from baseline at each scheduled time point and from baseline to nadir 2 hours post-randomization will be summarized by treatment group. Baseline is defined as the last assessment prior to randomization.

And exanet and UC will be compared by ANCOVA on the ranked percent change from baseline to nadir 2 hours post-randomization, adjusted for covariates of time from symptom onset to the baseline imaging scan (< 180 minutes versus \geq 180 minutes) and baseline anti-fXa activity. Missing data for this analysis will be handled as follows:

Section 6.1 details the handling of missing baseline data and data above and below the upper and lower limit of quantitation.

Participants with missing baseline value will be excluded from the analysis. Remaining missing data at 1 and 2 hours post-randomization will be imputed using the multiple imputation method described by Rubin (1967). Covariates included in the imputation model include treatment group, time, time-by-treatment interaction, and baseline anti-fXa activity. Based on the imputed datasets, nadir value and percent change from baseline to nadir will be derived. ANCOVA on the ranked percent change to nadir will be used to generate the p-value for comparing andexanet and UC. This imputation process will be run 100 times, and 100 p-values will be generated; the median p-value rule, as outlined in Eekhout et al (2017), will be applied to derive the final p-value.

Figures displaying the line plots of anti-fXa activity by treatment group at baseline and at 1 and 2 hours post-randomization and boxplots at baseline and nadir by treatment group will be presented overall and for each prior FXa inhibitor.

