- For start date: If the day is missing, then impute with 01, and if both the day and the month are missing, then impute with 01-Jan.
- For end date: If the day is missing, then impute with the last day of that month, and if both the day and the month are missing, then impute with the last visit/contact/survival/death day of study or Day 30.
- If the year is missing, then keep as is. No imputation is required if the complete date is missing.

Definition of Baseline Values

Baseline is defined as the most recent nonmissing assessment within the protocol-defined visit window prior to randomization. If there is no assessment within the visit window of randomization, then the assessment closest to randomization prior to treatment will be used as baseline. Data that are outside the baseline assessment windows specified above will not be excluded from analyses but will be identified as protocol deviations.

Start of Study Treatment

For and exampt treatment group, the start of study treatment will be the start of and exampt. For the UC treatment group, the start of study treatment will be the start of the specific UC drug received by the participant, or if the UC consists of no treatment, then the start of study treatment will be the randomization date for the participant.

Restart of Anticoagulants

The time when anticoagulants were restarted is defined as (date restart anticoagulation - date of the first study treatment) + 1. If the participant is assigned to UC and receive no treatment, then the date of the first study treatment will be replaced by the date of randomization. Oral anticoagulants will be summarized separately.

Study Day

For participants who are randomized to UC group and received no treatment, the study day is calculated based on randomization date. For events prior to randomization, the study day is calculated as date of event - date of randomization; for events on or after randomization, the study day is calculated as date of event - date of randomization + 1. For other participants, the study day is calculated based on the date of treatment initiation, using the same formula as above. Study day is referred as "day" in outputs.

Calculation of On Treatment Nadir

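### The SAP 6.1 baseline fallback stops at treatment start, not randomization, so it can select a post-randomization baseline, with an allowance of up to 30 minutes with andexanet and up to 3 hours with a usual-care drug

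*SAP*

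**What the plan says.** - SAP 6.1, Definition of Baseline Values, gives the main rule: "Baseline is defined as the most recent nonmissing assessment within the protocol-defined visit window prior to randomization". When no such value exists, the cut-off changes: "the assessment closest to randomization prior to treatment will be used as baseline". Out-of-window values stay in the analysis and are flagged as protocol deviations.
- SAP 6.1, Start of Study Treatment, dates treatment in the andexanet arm from the start of andexanet. In usual care, "the start of study treatment will be the start of the specific UC drug received by the participant". If usual care is no treatment, the randomization date is used.
- Protocol 3.1 says "Dosing procedures begin after randomization" and "Andexanet dosing should be initiated no later than 30 minutes after randomization". Usual care is whatever the treating team considers appropriate, "initiated within 3 hours post-randomization".
- For anti-fXa, SAP 5.4 says "Baseline is defined as the last assessment prior to randomization", and Protocol 10.5.4.3 agrees. SAP 5.4 excludes patients with no baseline, but refers to SAP 6.1 for the handling of missing baselines. There, a missing anti-fXa baseline is replaced by a baseline measurement taken outside the window. The rule does not say that this measurement must precede randomization.
- SAP 6.1, Calculation of On Treatment Nadir, takes the lower of the 1-hour and 2-hour anti-fXa values.

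**The concern.** The comparison is anchored at randomization: the protocol synopsis makes it time 0, and Protocol 3.3.2 ties all endpoint timing to it. A baseline taken later belongs to the follow-up being compared. When the time by which it may be late depends on the treatment received, change from baseline does not mean the same thing in the two arms.

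For anti-fXa, a later baseline in usual care removes part of the natural decline from the usual-care change score, which favors andexanet. For NIHSS and GCS, it would hide early deterioration in usual care, which works against andexanet. The anti-fXa endpoint matters most, because it is the only secondary endpoint and sits in the alpha-controlled hierarchy.

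**Working it through.** The plan states no figure to reproduce. The check compares timing rules and adds one illustration.

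**Step 1. Allowance after randomization** (SAP 6.1 treatment-start rules with the Protocol 3.1 limits)

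| Patient | Latest treatment start = latest fallback baseline |
|---|---|
| Andexanet, dosed on time | 30 min |
| Usual care with a drug | 180 min |
| Usual care, no treatment | 0 min |

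The ratio of the two non-zero limits is 180/30 = 6.

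**Step 2. Which scheduled assessments fall inside it** (Protocol Appendix A, ±15 min)

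- 1-hour anti-fXa and 1-hour thrombin generation: 60 ± 15 = 45 to 75 min.
- 2-hour anti-fXa, NIHSS and GCS: 120 ± 15 = 105 to 135 min.

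The earliest, 45 min, is later than 30 min, so none can precede andexanet given on time. All are earlier than 180 min, so any of them can precede a usual-care drug started late enough.

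**Step 3. When such a value would be chosen.** The fallback applies only if no in-window value exists, and it then takes the closest value.

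- Anti-fXa with a 15-minute window (synopsis, Appendix A): a sample less than 45 min before randomization always beats the 1-hour sample. One more than 75 min before always loses to a 1-hour sample that precedes treatment. Between 45 and 75 min, it depends on the actual times.
- Anti-fXa with a 120-minute window (Protocol 10.5.2): samples up to 120 min before randomization are in window, so the fallback is not reached. An earlier sample would lose to a 1-hour sample that precedes treatment.
- The 2-hour anti-fXa sample can be chosen only if there is no 1-hour sample, since the latter is always closer.
- NIHSS and thrombin generation (120-minute pre-randomization windows; Appendix A gives GCS the same): an out-of-window earlier value is more than 120 min away. It therefore loses to a pre-treatment 1-hour thrombin generation sample, and to a pre-treatment 2-hour score taken at 105 to 120 min.

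**Step 4. Effect on anti-fXa.** Let X1 and X2 be the 1- and 2-hour values. If X1 is baseline, percent change = 100 × (min(X1, X2) − X1)/X1. This cannot exceed 0, and equals 0 whenever X2 ≥ X1, because X1 is then both baseline and nadir.

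**Step 5. Illustration.** Assume first-order decline with half-life h and no reversal effect. The values of h are assumptions and are not in the documents. With baseline at b hours and nadir at 2 hours, change = 100 × (2^(−(2 − b)/h) − 1).

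| h | b = 0 | b = 0.5 | b = 1 | b = 2 |
|---|---|---|---|---|
| 6 h | −20.6% | −15.9% | −10.9% | 0% |
| 9 h | −14.3% | −10.9% | −7.4% | 0% |
| 12 h | −10.9% | −8.3% | −5.6% | 0% |

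The b = 2 column ignores the imputed 1-hour value that SAP 5.4 would supply. For an affected usual-care patient, a 1-hour baseline roughly halves the recorded natural decline.

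**The case against.** The strongest reply is that the anti-fXa endpoint has its own rules. SAP 5.4 requires a pre-randomization baseline and excludes patients without one. The substitution rule speaks of a baseline measurement taken outside its window, which most naturally means a sample drawn as baseline, and the nadir rule assigns the 1- and 2-hour samples to follow-up. On that reading, only a late baseline draw is at issue, and this can occur in either arm. The reading is reasonable, but the text does not settle it: SAP 5.4 hands missing baselines to SAP 6.1, and neither rule there requires the value to precede randomization.

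Other parts of the reply stand:

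- Protocol 3.1 wants all patients treated as soon as possible, so late usual-care starts may be uncommon.
- Eligibility under the current protocol depends on NIHSS and GCS at consent, so a patient with no earlier score should be rare.
- For the primary endpoint, SAP 6.1 sends cases with a missing or out-of-window baseline scan or NIHSS to the EAC unless they already count as failures. The per-protocol rules also list post-randomization baselines.

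A reader might infer that the problem exists in one arm only, or that any pre-treatment value may serve. Neither follows. Andexanet also starts after randomization, untreated usual care has no allowance, and the rule takes only the closest value when none is in window. A reader might also attach a count, for example 1% to 3% of 450 usual-care patients (4.5 to 13.5). The documents give no basis for that percentage.

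**Conclusion.** The point holds as a conflict between stated rules, with an arm-dependent effect when the fallback is triggered. The post-randomization allowance is 0 to 30 minutes with andexanet and 0 to 180 minutes with a usual-care drug. With andexanet dosed on time, scheduled follow-up assessments can become baseline only in usual care. This requires four things together: no in-window value, no closer pre-randomization value, an active usual-care drug, and a drug start after the assessment in question.

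The exposure is mainly the anti-fXa percent change, then change from baseline in ETP, NIHSS and GCS. The number of patients and the effect on the ranked ANCOVA cannot be derived, and the documents do not show that the secondary result would be materially biased. The directions also differ: toward andexanet for anti-fXa, against it where early NIHSS or GCS worsening in usual care is hidden. This is a minor point, worth correcting because the correction is cheap.

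**What to change.** Amend the SAP text as follows:

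1. In Definition of Baseline Values, end the fallback at randomization in both arms: use the last value before randomization, even if out of window. Never use a scheduled post-randomization assessment as baseline. If no earlier value exists, baseline is missing.
2. Put the same limit in the rule for missing anti-fXa baselines, so that it agrees with SAP 5.4 and Protocol 10.5.4.3.
3. State an exception for pre-morbid mRS, which Protocol 9.1.5 and SAP 5.5.3 allow to be collected after randomization.
4. Reconcile the anti-fXa baseline window (15 minutes in the synopsis and Appendix A, 120 minutes in Protocol 10.5.2), since it decides when the fallback applies.

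The post-randomization allowance then becomes 0 minutes in both arms. No new data are needed. The cost is that a few patients whose only baseline draw came just after randomization lose their baseline value and drop out of the affected analyses. A sensitivity analysis that readmits late baseline draws taken before treatment would show whether this matters. The number of such patients should be reported by arm.

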5.7.5. Hospitalizations

Hospitalization endpoints include the following:

- Length of the initial hospitalization for a primary bleeding event. The first duration (in hours) is from the initial hospitalization to randomization, and the second duration (in days) is from randomization to the first discharge date. The total duration from the initial hospitalization to the first discharge date will also be summarized.
- Total time (in days) admitted to the intensive care unit (ICU) during the initial hospitalization.
- Rate of rehospitalization, including the total number of rehospitalizations and the total number of days rehospitalized, at 30 days post-randomization.

The length of the initial (index) hospitalization, the total time spent in the ICU, and the occurrence of rehospitalizations (including the total number of rehospitalizations and the total number of days rehospitalized) up to 30 days post-randomization will be summarized descriptively by treatment group and total.

If the time between consecutive hospitalizations is < 6 hours apart and the discharge location for the first event is either an ICU or an "inpatient non-ICU" environment, then these events are considered to be a single hospitalization. If, however, the discharge location of the first event is home care, home hospice, long-term care hospital, intermediate care facility, outside hospital, or

other, then the subsequent event is to be considered a rehospitalization regardless of the time between the events.

By-participant listings of the initial hospitalization and rehospitalizations will be provided.

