On treatment nadir is the minimum anti-fXa activity post-randomization (ie, value observed at either 1- or 2-hour post-randomization evaluation). A percent reduction will be calculated as the ratio between the maximum reduction from baseline and the baseline value, multiplied by 100.

Length of Hospitalization and Rehospitalization

The following steps will be followed to calculate the length of hospitalization (or rehospitalization):

- The length of stay (LOS) will be calculated as discharge date/time admission date/time + 1.
- If the participant admission time and the discharge time are missing and the dates are the same, the LOS will be assumed to be 1 day.
- If the participant admission time and the discharge time are missing and the dates are not the same, the LOS will be calculated using the date portion of the dates plus 1.
- If the discharge date is missing and there is no new admission date, the date of the 30-day visit or the date of death (whichever is earlier) will be imputed as the discharge date.
- If the participant has withdrawn consent, the discharge date will be imputed as the date of the 30-day visit or the date of death (whichever is earlier and/or available).

Neurologic Deterioration at 24 hours

Neurologic deterioration at 24 hours is defined as an NIHSS increase \geq 4 at 24 hours compared to baseline or a GCS score decrease \geq 2 at 24 hours compared to baseline.

Neurologic Deterioration at 12 hours

Neurologic deterioration at 12 hours is defined as an increase of \geq 7 point from baseline to 12 hours in NIHSS.

Utility-Weighted mRS

Mean utility values will be based on EQ-5D-5L at the same visit and will be determined by averaging the utilities of all participants within each mRS category.

AEs With Partial or Missing Start and End Date

If the start date of an AE is partially or completely missing and the end (stop) date and time of the AE do not indicate that it occurred prior to the first dose, then the determination of treatmentemergent status will be based on the following:

- If the start year is after the year of the first dose, then the AE is treatment emergent.
- If the start year is the same as the year of the first dose and:
 - If the start month is missing, then the AE is treatment emergent.
 - If the start month is present and is the same as or after the month of the first dose, then the AE is treatment emergent.

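### The SAP's length-of-stay rule adds 1 to a date/time difference, so stays with both times recorded match neither elapsed time nor a calendar-day count

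*SAP*

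**What the plan says.** SAP 6.1, under the heading on length of hospitalization and rehospitalization, gives the main rule: "The length of stay (LOS) will be calculated as discharge date/time admission date/time + 1". The operator between the two date/times is missing from the text available to this review. I read it as a minus sign and make nothing of its absence. The introductory line applies the rule to index stays and to rehospitalizations.

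Two fallbacks follow for missing times. The first reads: "If the participant admission time and the discharge time are missing and the dates are the same, the LOS will be assumed to be 1" (the unit given there is days). In the second, where the dates differ, "the LOS will be calculated using the date portion of the dates plus 1". Later bullets impute a missing discharge date from the 30-day visit or the date of death.

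SAP 5.7.5 describes what is reported. For the index stay: "The first duration (in hours) is from the initial hospitalization to randomization, and the second duration (in days) is from randomization to the first discharge". It adds: "The total duration from the initial hospitalization to the first discharge date will also be summarized". For readmissions the endpoint is: "Rate of rehospitalization, including the total number of rehospitalizations and the total number of days rehospitalized, at 30 days post-randomization". ICU time is a separate item: "Total time (in days) admitted to the intensive care unit (ICU) during the initial hospitalization". All of these are summarized descriptively (SAP 5.7.5; Protocol 10.6.5).

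**The concern.** Adding 1 to a difference between dates counts both the first and the last calendar day. Adding it to a difference that already carries clock times has no such meaning; it lengthens the measured duration by one day. The SAP's wording suggests that the main rule really does use times. It writes date/time there, gives separate fallbacks that use only the date portion, and elsewhere in SAP 6.1 (study day, restart of anticoagulants) writes plain date where it wants inclusive counting. Nothing says that times are dropped first.

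Length of initial hospitalization and total days rehospitalized are listed safety endpoints (Protocol Table 1 and 10.6; SAP Table 1). Their reported values would depend on a mixed convention, and the total of rehospitalized days would carry an excess equal to the number of timed readmissions.

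**Working it through.** **Inputs.** The three LOS rules in SAP 6.1 and the durations in SAP 5.7.5. The main rule gives no unit; days is inferred from the fallback that assigns 1 day. Clock times and stay lengths below are assumed for illustration, because the documents give none.

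**The plan's own figure.** Same date, times missing: date difference 0 + 1 = 1 day. This matches the SAP.

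**Formulas.**
- Elapsed days: E = (discharge date/time - admission date/time in hours) / 24
- SAP rule with both times: E + 1
- Inclusive calendar days (the SAP fallback): D + 1, where D = discharge date - admission date

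| Stay | E | SAP rule, E + 1 | Inclusive, D + 1 | SAP rule minus inclusive |
|---|---|---|---|---|
| 08:00 to 14:00, same day | 0.25 | 1.25 | 1 | +0.25 |
| 10:00 to 10:00 next day | 1.00 | 2.00 | 2 | 0.00 |
| 20:00 to 08:00 next day | 0.50 | 1.50 | 2 | -0.50 |
| Day 1 16:00 to day 11 11:00 | 9.79 | 10.79 | 11 | -0.21 |

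Against elapsed time the excess is (E + 1) - E = 1 day for every timed stay. Against the inclusive count the difference is (E + 1) - (D + 1) = E - D, which is the discharge clock time minus the admission clock time, in days. It lies between -1 and +1.

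**Rehospitalized days.** With k timed readmissions the total rises by k:
- one readmission: 2.5 + 1 = 3.5 days
- two readmissions: 4.0 + 2 = 6.0 days
- three readmissions: 4.5 + 3 = 7.5 days

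**Index stay.** Take 3 hours before randomization and 9.8 days after it, both as elapsed times. The parts sum to 3/24 + 9.8 = 9.925 days. If the total is derived with the LOS rule it is 10.925 days, so the parts and the total disagree by 1 day.

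**Timed against untimed stays.** For a stay without times, the fallback exceeds elapsed time by (D + 1) - E = 1 - (discharge clock time - admission clock time), between 0 and 2 days. If clock times are assumed uniform and independent, the average is 1.0. So the timed and untimed branches agree on average under the present rule, though not patient by patient.

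**The case against.** The best defence is that the SAP mostly counts days inclusively. Study day on or after randomization, restart of anticoagulants and the untimed LOS fallback all add 1. Against that convention a timed stay is off only by a clock-time difference and is not systematically a day too long. This stands in part: the one-day excess is an excess over elapsed time only. But the timed rule does not deliver inclusive days either, since it returns 1.25 or 10.79 where an inclusive count returns 1 or 11. SAP 5.7.5 speaks of durations, reports the first part of the index stay in hours and merges stays by a gap in hours, and Protocol Appendix A has sites record hours. These all point towards elapsed time.

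A second objection also stands. Dropping the 1 only from timed stays would put timed and untimed stays about one day apart on average, where they now roughly agree. The remedy has to cover every branch.

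A reader might infer more than the documents support:
- **ICU time is inflated too.** The LOS rule names hospitalization and rehospitalization only, and SAP 5.7.5 lists ICU time separately with no added day. ICU time is affected only if programmers reuse the rule for it.
- **Every stay is a day too long, so three days reported as four is a 33% error.** The excess is exactly 1 day only where both times are recorded, and only against elapsed time. Four can be the correct inclusive count for such a stay.
- **One day is added to each part of the index stay.** Nothing in SAP 5.7.5 says so. The mismatch shown above arises only if the rule is used for the total.

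**Conclusion.** The point holds as a minor defect in a derived variable. As written, SAP 6.1 reports each stay with both times recorded exactly 1 day above its elapsed duration and adds 1 day per timed readmission to total rehospitalized days. It also fails to reproduce an inclusive calendar-day count for individual patients, by up to a day either way. This rests on reading the missing operator as subtraction and the unit as days.

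The consequences are limited to descriptive safety summaries; no primary or secondary inference is touched. The shift cancels in the between-arm difference in mean index stay if times are recorded equally often in both arms. It does not cancel in total rehospitalized days if readmission counts differ, although the number of rehospitalizations is reported alongside and would let a reader see why.

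**What to change.** State in SAP 6.1 that LOS is in days, and use one convention in every branch. Either option works:

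1. **Elapsed days.** Use (discharge date/time - admission date/time in hours) / 24 when both times are known. Change the fallback to match: the date difference without the added 1, with a stated value for same-date stays, which would otherwise be 0.
2. **Inclusive calendar days.** Use discharge date - admission date + 1, computed from dates only, for all stays whether or not times exist.

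Apply the chosen convention to stays with only one time known, which SAP 6.1 does not address explicitly, and to stays with an imputed discharge date. Say whether ICU time follows the same rule. The elapsed option fits the split of the index stay in SAP 5.7.5 more naturally, because parts and total then add up.

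The cost is a few lines in the derivation and its program. Under the elapsed option, values for stays without recorded times are approximate.
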